6.12.1. Extent of Exposure

6.12.1.1. Duration of Exposure

Duration of exposure to study treatment (defined as time since first injection of study treatment in days) will be summarized by treatment group during the Induction Period, the Maintenance Period, and the combined Induction Period, Maintenance Period, and Rescue Period.

Duration of exposure during the Induction Period will be calculated as:

$$(Date\ of\ last\ study\ visit\ in\ the\ Induction\ Period - Date\ of\ first\ injection\ of\ study\ treatment + 1)$$

Duration of exposure during the Maintenance Period will be calculated as:

$$(Date\ of\ last\ study\ visit\ in\ Maintenance\ Period - Date\ of\ last\ study\ visit\ in\ the\ Induction\ Period + 1)$$

Duration of exposure during the Rescue Period will be calculated as:

$$(Date\ of\ last\ study\ visit\ in\ Rescue\ Period - Date\ of\ First\ Rescue\ Treatment + 1)$$

Duration of exposure to LY3074828 for the combined Induction Period, Maintenance Period, and Rescue Period will be calculated as:

$$(Date\ of\ last\ study\ visit\ in\ the\ Maintenance\ Period - Date\ of\ first\ injection\ of\ LY3074828 + 1)$$

for subjects without rescue and

$$(Date\ of\ last\ study\ visit\ in\ the\ Rescue\ Period - Date\ of\ first\ injection\ of\ LY3074828 + 1)$$

for subjects with rescue

For the combined Induction Period, Maintenance Period, and Rescue Period summaries, exposure will be summarized for all LY3074828 dosing regimens pooled.

Descriptive statistics will be provided for patient days of exposure and the frequency of patients falling into the following different exposure ranges (that is, only the exposure ranges that fall within the treatment period will be presented) will be summarized:

- >0, ≥7 days, ≥14 days, ≥30 days, ≥60 days, ≥90 days, ≥120 days, ≥183 days, ≥365 days, ≥548 days.
- >0 to <7 days, ≥7 to <14 days, ≥14 to <30 days, ≥30 to <60 days, ≥60 to <90 days, ≥90 to <120 days, ≥120 to <183 days, ≥183 to <365 days, ≥365 days to <548 days, and ≥548 days.

Additional exposure ranges may be considered if necessary.

A by-patient listing of exposure duration will be provided.

No inferential analysis for comparison between treatment arms will be performed.

6.12.1.2. Total Dose of active study treatment

The total number of active injections of LY3074828 will be summarized by LY3074828 treatment group.

Mean and median total dose will be reported for all the treatment groups.

Total dose of active study treatment during the Induction Period, the Maintenance Period, and the combined Induction Period, Maintenance Period, and Rescue Period will be summarized by active treatment group using descriptive statistics. The total dose (mg) will be calculated as:

$$\text{Total Dose} = \text{Sum over all injections received of [dose of LY3074828 (mg) prescribed per injection]}$$

The injections received during the treatment periods will be identified using the response to the question "Was study drug administered to patient?" on the Study administration eCRF page. The total dose of LY3074828 will then be calculated for each treatment group based on the injection schedule in the study protocol.

No inferential analysis for comparison between treatment arms will be performed.

6.12.2. Adverse Events

Adverse events will be classified based upon the latest version of the Medical Dictionary for Regulatory Activities (MedDRA). AEs will be recorded at every study visit. Conditions starting on or after the date of informed consent will be considered an AE. Preexisting conditions which worsens in severity on or after the date of informed consent will be considered and recorded as an AE on the AE electronic case report form (eCRF) page from the date of worsening onwards.

A treatment-emergent adverse event (TEAE) is defined as an event that first occurred or worsened in severity after baseline as defined in Section 6.1.2. Both the date/time of the event and the date/time of the dose (that is, injection) are considered when determining TEAEs. TEAE will be assigned to the study period to which it's considered treatment-emergent:

- The MedDRA lowest level term (LLT) will be used when classifying AEs as treatment-emergent.
- The maximum severity recorded for each LLT prior to the first dose date/time in the Induction Period will be used as the pretreatment severity for that LLT. If an event during the baseline period has missing severity, and the event persists during the treatment period, then it will be considered as treatment-emergent, regardless of the postbaseline level of severity. Events with a missing severity during the treatment period will be considered treatment-emergent.
- AEs with a particular LLT will be classified as treatment-emergent if they first start on or after the first dose date/time in the treatment period (that is, a patient has no preexisting conditions with that lowest level term), or if the severity is greater than the pretreatment severity for that lowest level term. If a partial AE start date/time is present, the date/time will be compared as far as possible to the treatment start date/time in order to determine whether the event is treatment-emergent or not. If there is any doubt, the event will be flagged as treatment-emergent.

A follow-up emergent adverse event is defined as an event that first occurred or worsened in severity after the date of Visit 29 or early termination visit (ETV):

- The MedDRA LLT will be used when classifying AEs as follow-up emergent.
- For AEs that are ongoing at the date of Visit 29 or ETV, the maximum severity recorded for each LLT on or prior to the date of Visit 29 or ETV will be used as the follow-up baseline severity for that LLT.
- If a partial AE start date is present, the date will be compared as far as possible to the date of Visit 29 or ETV in order to determine whether the event is follow-up emergent or not. If there is any doubt, the event will be flagged as follow-up emergent, unless the same event was already counted as treatment-emergent during the Induction Period.

Adverse events and TEAEs will be summarized and analyzed for the safety population for the Induction Period. Treatment comparisons between all Induction Period LY3074828 dose regimens (300 mg, 100 mg, 30 mg) combined and placebo will be conducted using Fisher's exact test. Resulting p-values will be used to help identify potential adverse drug reactions. Significant p-values will need to be interpreted with caution due to the fact that multiplicity is not controlled in this study.

Maintenance Period adverse events and TEAEs will be summarized by treatment. Follow-up emergent adverse events and TEAEs during the Rescue Period will be summarized in the All Periods safety analyses.

Additionally,

- An overall summary of AEs including the number and percentage of patients who experienced TEAE, TEAE by maximum severity, death, SAE, discontinuations from the treatment due to an AE, and TEAEs of special interest.
- TEAE by system organ class (SOC) and PT.
- TEAEs related to study treatment by SOC and PT
- TEAE by maximum severity, SOC, and PT.

If a safety event occurred on the same date of the last date of Induction and the first date of the Maintenance Period, the event will be allocated to the Maintenance Period only.

If a safety event occurred on the same date of the last date of Maintenance and the first date of Rescue, compare the event onset time with rescue dose time to allocate the event to the Maintenance Period or Rescue Period accordingly; if either time is missing, the event will be allocated to the Rescue Period only.

If a safety event occurred on the same date of the last date of Maintenance or Rescue and the first date of the Follow-up Period, the event will be allocated to the previous period (Maintenance or Rescue) only.

In general, for all AE related summaries, the number and percentage of patients experiencing the events will be presented by dosing regimen. The events will be ordered by decreasing frequency in the total LY3074828 group, followed in the order of 300 mg, 100 mg, 30 mg, within SOC and/or PT for sorting. For events that are gender-specific (as defined by MedDRA), the denominator and computation of the percentage will include only patients from the given gender.

A by-patient listing of all AEs will be provided.

6.12.2.1. Common Adverse Events

The percentages of patients with TEAEs will be summarized by treatment using MedDRA Preferred Term for the common TEAEs (occurred in $\geq 5\%$ before rounding of treated patients). Events will be ordered by decreasing frequency within System Organ Class.

The percentages of patients with TEAEs by maximum severity will be summarized by treatment using MedDRA Preferred Term nested within System Organ Class for the common TEAEs. For each subject and TEAE, the maximum severity for the MedDRA level being displayed (Preferred Term, High Level Term, or System Organ Class) is the maximum postbaseline severity observed from all associated LLTs mapping to that MedDRA level. These summary tables will be provided for the Induction Period.

In the event differential dropout rates are seen or to further investigate events of interest, summary tables comparing exposure-adjusted incidence rate (that is, person-time-adjusted incidence rates) over the entire time period will be generated for the Induction and Maintenance Periods.

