5.1. Summary of Study Design

Study AMAF is a multicenter, randomized, parallel-arm, placebo-controlled trial with 4 study periods in subjects with moderate-to-severe plaque psoriasis.

[figure not shown]
Screening Period (≤4 weeks): Subjects will be evaluated for study eligibility ≤28 days before the baseline visit (Visit 2/Week 0). At the baseline visit (Visit 2), subjects who fulfill the eligibility criteria will be randomized to 1 of 4 induction treatment arms.

Induction Period (16 weeks): A double-blind, 16-week Induction Period is designed to establish the efficacy and safety of LY3074828 administered at Visit 2 (Week 0) and Visit 5 (Week 8). Subjects will be randomized to 1 of 4 induction treatment arms (LY3074828 30 mg SC, LY3074828 100 mg SC, LY3074828 300 mg SC, and placebo every 8 weeks [Q8W]) stratified on the basis of previous exposure to biologic therapy for treatment of psoriasis.

Maintenance Period (88 weeks): The Maintenance Period consists of 88 weeks of treatment. At the end of the Induction Period (Week 16), subjects will continue treatment in the Maintenance Period which is intended to explore 1 of 2 treatment strategies through Week 104. All placebo subjects and subjects assigned to treatment with LY3074828 who have a <90% improvement in Psoriasis Area and Severity Index (PASI) from baseline (PASI 90) at Week 16 will receive LY3074828 300 mg SC Q8W during the entire Maintenance Period. Subjects with ≥PASI 90 PRN dosing group) at Week 16 will only be dosed with LY3074828 at the baseline dose level assignment no more frequently than Q8W when disease activity level is <PASI 90, and this will continue until ≥PASI 90 is regained.

Follow-up Period (16 weeks): The Follow-up Period will include a visit every 4 weeks for a total of 16 weeks following Visit 29 to assess subject safety and study drug efficacy.

[Figure 5.1](#) illustrates the study design.

^a Visits will occur every 4 weeks in the Maintenance and Follow-up Periods.
 Abbreviations: PASI = Psoriasis Area and Severity Index; PRN = as needed; Q8W = every 8 weeks.

Figure 5.1. Illustration of study design for Clinical Protocol I6T-MC-AMAF.

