5.2. Determination of Sample Size

Approximately 200 subjects will be randomized at a 1:1:1:1 ratio in the blinded induction dosing period to LY3074828 30 mg, 100 mg, 300 mg, and placebo (50 subjects per dosing regimen, respectively). Randomization will be stratified by prior exposure to biologic therapy for psoriasis (yes/no).

Assuming 60% and 3% PASI 90 response rates at 16 weeks for LY3074828 and placebo, respectively, pairwise comparisons to placebo have over 99% power using a 2-sided Fisher's exact test at the 0.05 significance level, with no adjustment for multiple comparisons.

As results for PRN dose arms in the Maintenance Period will support the maintenance dosing strategy in Phase 3 planning, a reasonable total number of subjects who completed 1-3 visits in the Maintenance Period (Week 20 to Week 28) will be needed. Based on study simulations under the treatment effect scenario outlined above, approximately 49 subjects (9 on 30 mg, 18 on 100 mg, 22 on 300 mg PRN arms) will have completed the Week 20 visit at the time of the primary endpoint datalock.

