6.1.2. Definitions

6.1.2.1. Study Time Intervals

Induction Period

All subjects who were randomized to the study are considered as entering the Induction Period.

The start of the Induction Period is defined as the date of first injection following randomization. For subjects who were randomized but not dosed, the Induction Period starts at the randomization date.

The end of the Induction Period is defined as the date of PASI measurement at Week 16, or the early termination date if subjects discontinued from study prior to or at Week 16, or Day 117, whichever comes first.

Maintenance Period

All subjects who had Week 16 visit with PASI measurement (except the ones discontinued the study at Week 16) are considered to have entered the Maintenance Period.

The start of the Maintenance Period is defined as the same date as end of the Induction Period, which is the date of PASI measurement at Week 16.

The end of the Maintenance Period is defined as the visit date at Week 104, or the date when the subjects received rescue treatment, or the early termination date if subjects discontinued from study prior to or at Week 104, whichever comes first.

Rescue Period

All subjects in PRN groups who received at least 1 dose of rescue treatment are considered to have entered the Rescue Period, and will be included in the Rescue Period analysis population.

The start of the Rescue Period is defined as the date the patient received the first dose of rescue treatment.

The end of the Rescue Period is defined as the visit date at Week 104, or early termination date if subjects discontinued from study prior to or at Week 104, whichever comes first.

Follow-up Period

All subjects who had Visit 29 are considered to have entered the Follow-up Period, and will be included in the Follow-up Period analysis population.

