6.12. Safety Analyses

All safety evaluations will be based upon the Safety Population as defined in Section [6.1.1](#).

Safety and tolerability will be evaluated in terms of adverse events (AEs), treatment-emergent AEs (TEAEs), discontinuations due to AEs, deaths, other SAEs, permanent discontinuations and interruptions of study drug, laboratory analyses including neutrophil counts and immunogenicity, Columbia Suicide Severity Rating Scale (C-SSRS), vital signs, echocardiogram (ECG) findings, and concomitant medications.

The Induction Period safety analyses will summarize each LY3074828 dose regimen (300 mg, 100 mg, and 30 mg) and compare the pooled LY3074828 dose regimens to placebo. Treatment group comparisons will be analyzed using the methods described in Section [6.1.3](#).

For the Maintenance Period, safety will be summarized by treatment (each PRN arm and 300 mg Q8W). No comparisons will be conducted. Only events occurred in the Maintenance Period will be included in this analysis, that is, no events in the Rescue Period will be included. Only a

smaller set of safety analyses (for example, TEAE, serious adverse events (SAE), AE leading to study treatment discontinuation, TE high/low labs, TE high/low vitals) will be needed for the Maintenance Period.

In addition, an overall summary of safety for all LY3074828 exposed subjects, will be provided by presenting all LY3074528 arms pooled including the Induction, Maintenance, and Rescue Periods; Follow-Up Period separately (if there are meaningful number of subjects); and All Periods + Follow-up Period. Only a smaller set of safety analyses (for example, TEAE, SAE, AE leading to study treatment discontinuation, TE high/low labs, TE high/low vitals) will be needed for the overall safety summary.

Safety event occurring on the same day of the end of a period and the start of next period will be counted towards the next period, for example, if a safety event occurred on the date of PASI measurement at Week 16, the event will be allocated to the Maintenance Period.

Change from baseline analyses will use baseline definition provided in Section 6.1.2.

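### Maintenance adverse events are reported as crude percentages although rescue cuts short time at risk in the PRN arms only, and rescue is not a named trigger for exposure-adjusted rates

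*SAP*

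**What the plan says.** **Time at risk.** SAP 5.1: "The Maintenance Period consists of 88 weeks of treatment". Under SAP 6.1.2.1 a subject's Maintenance Period ends at the earliest of the Week 104 visit, "the date when the subjects received rescue treatment", or early termination. Only PRN subjects can be rescued (Protocol 7.8.2; SAP Table 5.1). They then stay on the rescue regimen to the end of the study.

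**Events counted.** Maintenance safety is summarized for each PRN arm and for 300 mg Q8W, without comparisons. SAP 6.12: "Only events occurred in the Maintenance Period will be included in this analysis, that is, no events in the Rescue Period will be included". TEAEs in the Rescue Period go to the All Periods analyses (SAP 6.12.2), which combine all LY3074828-exposed subjects (SAP Table 6.1).

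**Metric.** AE summaries give counts and percentages of patients by dosing regimen (SAP 6.12.2). SAE tables do the same and cover Maintenance (SAP 6.12.3).

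**Person-time rates.** SAP 6.12.2.1: "In the event differential dropout rates are seen or to further investigate events of interest, summary tables comparing exposure-adjusted incidence rate" are to be generated for the Induction and Maintenance Periods. SAP 6.12.3 has parallel wording for serious events. There are two triggers, neither is defined, and neither mentions rescue.

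**Exposure.** Duration of exposure is summarized by treatment group for Maintenance without any condition (SAP 6.12.1.1).

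**The concern.** A rescued PRN subject stays in the percentage denominator but stops contributing time and events at rescue. A Q8W subject is never cut short in this way. Rescue follows inadequate response, and the doses were chosen to span minimal to maximal effect (Protocol 5.5), so unequal rescue across the PRN arms is plausible. An arm that fails early would then show fewer subjects with events for a reason unrelated to safety.

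The efficacy analyses handle rescue explicitly: non-response after rescue (SAP 6.3.1), exclusion of later visits from the MMRM (SAP 6.3.2) and censoring at rescue (SAP 6.1.3). The Maintenance AE percentages have no matching adjustment. At stake is a side-by-side safety table from PRN arms whose results, according to SAP 5.2, will support maintenance dosing plans for Phase 3.

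**Working it through.** **The plan's own figures.** The documents give no figure for rescue or for adverse event rates. The one checkable design figure is the power in SAP 5.2. It rests on 50 per arm ("Approximately 200 subjects will be randomized at a 1:1:1:1 ratio in the blinded induction dosing period"), on response rates ("Assuming 60% and 3% PASI 90 response rates at 16 weeks for LY3074828 and placebo"), and on a two-sided Fisher's exact test "at the 0.05 significance level, with no adjustment for multiple comparisons". Exact enumeration gives 0.9999999, so the stated value of over 99% reproduces. It has no bearing on this point.

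**Inputs from the documents**
- Maintenance runs from Week 16 to Week 104: 104 − 16 = 88 weeks.
- PRN subjects are evaluated at every visit from Week 20 and dosed no more often than every 8 weeks (Protocol 2 and 5.1).
- Rescue is possible after three consecutive retreatment doses without regaining PASI 90, or below PASI 50 after one retreatment dose (Protocol 7.8.2).

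**Inputs assumed**
- First loss of response at Week 20. Three doses at Weeks 20, 28 and 36 put rescue at Week 44, that is 44 − 16 = 28 weeks into Maintenance. The PASI 50 route could put it near Week 28, or 12 weeks in.
- Share rescued r = 30%.
- Constant first-event hazard h of 0.1 to 1.0 per person-year, the same in both groups and unrelated to rescue. No other discontinuation.

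**Time lost by a rescued subject.** 1 − 28/88 = 68%, and 1 − 12/88 = 86%.

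**Percentage with an event** (52.18 weeks per year)
- No rescue: F = 1 − exp(−h × 88/52.18)
- Rescued at 28 weeks: R = 1 − exp(−h × 28/52.18)
- PRN arm: 0.7 × F + 0.3 × R

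| h per year | F | R | PRN arm | Gap, points |
|---|---|---|---|---|
| 1.0 | 0.815 | 0.415 | 0.695 | 12 |
| 0.3 | 0.397 | 0.149 | 0.323 | 7 |
| 0.1 | 0.155 | 0.052 | 0.124 | 3 |

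**Exposure-adjusted rate.** Mean time to first event or censoring is the proportion with an event divided by h. At h = 0.3 it is 0.397/0.3 = 1.32 years without rescue and 0.323/0.3 = 1.08 years in the PRN arm. Events divided by time return 0.30 per year in both, so the gap disappears.

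**Range.** A wider grid (52-week year; 10% to 75% rescued at 12, 28 or 52 weeks; h of 0.1 to 1.0) lowers the percentage by 0.6 points (h = 0.1, 10% rescued at 52 weeks) to 45.7 points (h = 1.0, 75% rescued at 12 weeks). With 50% rescued at 28 weeks and h of 0.1 to 0.5 in the group without rescue, a true hazard ratio of about 1.55 to 1.73 against the PRN arm would show as equal percentages.

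**The case against.** The strongest reply is that this is a descriptive Phase 2 table and the plan already has most of what is needed.

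- **Rates are already provided for.** A reader might infer that person-time rates appear only if dropout differs. The documents do not support that: both sentences carry a second trigger, to investigate events of interest. It narrows the gap without closing it. It is discretionary and event-specific, and an event may attract no interest because truncation lowered its percentage.
- **Unequal exposure will be visible.** This stands. Maintenance exposure duration is always tabulated by group, and PRN doses are summarized by arm (SAP 6.9.3). But first-event rates for individual terms cannot be recovered from mean duration.
- **Events after rescue are not lost.** This stands. They are in All Periods and in the by-patient listing, and ending attribution to the PRN dose at rescue is reasonable. The All Periods summary is pooled, so it does not restore the view by arm.
- **The groups are not comparable anyway.** This stands. PRN subjects are Week 16 PASI 90 responders; Q8W holds the active-arm non-responders and all placebo subjects. A reader might infer that rates would permit a PRN against Q8W comparison. They would not. They remove only the artefact of unequal follow-up.
- **The illustrated gap is small in subjects.** Under the SAP's 60% response a PRN arm has 0.6 × 50 = 30 subjects. The gap at h = 0.3 is about 2 of them, and the standard error of one 40% proportion is √(0.4 × 0.6/30) = 9 points. This limits the priority, but the artefact is systematic and has a known direction.

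A reader might also infer that undosed PRN time is wrongly counted as exposure, because SAP 6.12.1.1 uses "defined as time since first injection of study treatment in days", and that PRN person-time should be split at 3 months after the last dose. The documents do not support that either. Maintenance has its own formula, starting at the last Induction visit. PRN dosing is the strategy under study, so time on strategy is a legitimate denominator. The 3-month interval comes from the contraception criteria (Protocol 6.1), not from a safety risk window.

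**Conclusion.** The point holds as a cheap improvement. By the SAP's own definitions, Maintenance AE and SAE percentages depend on how much rescue an arm has and how early. Neither trigger for exposure-adjusted rates is sure to respond, because rescued subjects remain in the study and rescue is not named.

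The direction follows if rescue is unequal and the hazard is roughly constant and unrelated to rescue. The size is not derivable from the documents. The 32% against 40% rests on an assumed 30% rescued at 28 weeks and 0.3 events per year, and it would be smaller with rarer or later rescue. A reader might infer that the plan will make a failing PRN dose look safer. The documents support only that it could, since they give no rescue rates and exposure by group will be on view.

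**What to change.** In SAP 6.12.2, 6.12.2.1 and 6.12.3:

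- Make exposure-adjusted incidence rates standard in Maintenance for TEAEs, SAEs, discontinuations due to AE and special-interest events, in place of the conditional wording.
- Define time at risk as ending at the earliest of first event, rescue, discontinuation or Week 104.
- Print person-time beside each percentage.
- State that the Maintenance groups are defined by Week 16 response, so the rates are descriptive and do not make PRN and Q8W comparable.

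No split of PRN person-time by interval since the last dose is needed. The required dates already feed the period and exposure definitions, so nothing new is collected. The cost is SAP wording and extra table columns to produce and review.
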